For statistical analysis of quantitative features, compliance with the normal distribution law will be preliminarily assessed by one of the generally accepted methods (Shapiro-Wilk criterion). When testing statistical hypotheses for indicators with a normal distribution, parametric criteria will be used, and for indicators whose distribution differs from normal, nonparametric criteria will be used.

The following indicators will be calculated as descriptive statistics parameters for continuous (quantitative) data:

- n number of valid observations;
- M, Mean arithmetic mean;
- Me, Median median;
- Min minimum value;
- Max maximum value;
- Q1 lower quartile;
- Q3 upper quartile;
- Range range;
- IQR interquartile range;
- SD standard deviation;
- SE standard error of the mean;
- w Wilcoxon-Mann-Whitney test for independent groups;
- t Student's t-test with Welch's correction for independent groups;
- f Fisher's exact test;
- $\gamma 2$ Chi-square test.

For ordinal, categorical and qualitative variables:

- absolute frequency (number of observations);
- relative frequency (expressed as a percentage).

The results of the assessment of quantitative variables, the distribution of which corresponds to the law of normal distribution, will be presented as M±SD, where M is the mean value, and SD is the standard deviation. The results of the assessment of quantitative variables, the distribution of which does not correspond to the law of normal distribution, will be presented as Me [Q1; Q3], where Me is the median, and Q1 and Q3 are the lower and upper quartiles.

Efficacy and safety indicators, as well as their changes, will be presented using descriptive statistics by visits and therapeutic groups. For study visits, qualitative (dichotomous) indicators will be compared between groups based on the Pearson $\chi 2$ criterion, the Pearson $\chi 2$ criterion with Welch's correction, or the Fisher exact test for tables of arbitrary dimension (if the frequency of the indicator in at least one of the subgroups is 5 or less).

Comparison of groups by quantitative indicators can be carried out using the Student's T-test and the Mann-Whitney test. Comparison of intra-group parameters before and after treatment can be

performed using the T-test for related samples or the Wilcoxon-Mann-Whitney test. Statistically significant values are p-level <0.05.

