Safety analysis will be performed for the safety population. The following safety parameters are provided for in this study:

- Total number of AEs, stratified by severity and frequency;
- Frequency of AEs, related, in the opinion of the physician-investigator, to the use of the study drug;
- Frequency of serious adverse events (SAEs), related, in the opinion of the physician-investigator, to the use of the study drug;
 - Proportion of patients with at least one AE;
 - Proportion of patients with 2 or more AEs.

The dynamics of quantitative safety parameters relative to baseline values will be assessed and compared with each other using ANOVA with repeated measures. This method allows to simultaneously check for statistically significant dynamics (at least one average value at one time point differs from the others), and also to compare the dynamics and ranges of the indicator values when obtaining the compared drugs. In case of inappropriateness of the use of parametric methods, a similar analysis of the change in the distribution of indicators during therapy will be carried out using non-parametric analogues - the Friedman criterion and the Wilcoxon signed rank criterion, and intergroup comparisons of changes - using the Wilcoxon-Mann-Whitney criterion.

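### The SAP names an independent-groups rank test for within-arm before/after comparisons of non-normal indicators; with positively correlated visits, its true error rate under no change falls below 5%

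*Combined protocol and SAP*

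**What the plan says.** The Statistical Analysis Plan first sets a general rule: after a Shapiro-Wilk check, "for indicators whose distribution differs from normal, nonparametric criteria will be used". It then assigns tests by type of comparison.

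- Between arms: "Comparison of groups by quantitative indicators can be carried out using the Student's T-test and the Mann-Whitney test".
- Within an arm: "Comparison of intra-group parameters before and after treatment can be" "performed using the T-test for related samples or the Wilcoxon-Mann-Whitney test".

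In its list of statistics the SAP describes the latter rank test as the "Wilcoxon-Mann-Whitney test for independent groups".

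The safety section handles the same question differently. Its scope is set by the sentence "The dynamics of quantitative safety parameters relative to baseline values will be assessed". Where parametric methods do not suit, it names "the Friedman criterion and the Wilcoxon signed rank criterion" for change during therapy, and "intergroup comparisons of changes - using the Wilcoxon-Mann-Whitney criterion".

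**The concern.** Before and after values in one arm come from the same patients. The Mann-Whitney reference distribution assumes two independent samples, so it uses the wrong variance when the visits are correlated. If the correlation is positive, as one would usually expect for repeated scores, the assumed variance is too large. The test then rejects less often than the stated 5% when nothing has changed, and it can miss a real change that a paired test would find.

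The general rule sends non-normal indicators to nonparametric tests, and only one is named for within-arm use, so an analyst following the text literally would run an unpaired test on paired data. The safety paragraph gets the split right, but nothing extends it to the efficacy scales. At stake are the within-arm p-values of non-normal indicators outside the safety section, and nothing wider.

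**Working it through.** **Inputs from the documents.** Enrolment of 60 with 1:1 allocation (Study Design) gives 60 / 2 = 30 pairs per arm if nobody drops out. The significance threshold is 0.05 (SAP); sidedness is not stated, so two-sided is assumed.

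**Inputs assumed.** Between-visit correlation, distribution and size of change. The documents give none of these, so ranges are shown.

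**Calibration.** The plan has no power or sample-size figure to reproduce; the only anchor is 0.05. With zero correlation between visits, the simulated Mann-Whitney test (30 vs 30, 20,000 replicates) rejects in 4.7% to 5.0% of samples across normal, lognormal and skewed integer data. The test is sound when its independence assumption holds.

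**Size by formula.** With Spearman correlation ρ_S between visits and no change, the true standard deviation of the Mann-Whitney statistic is about √(1 − ρ_S) times the value the test assumes. So

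actual α ≈ 2 × P(Z > 1.96 / √(1 − ρ_S)), with ρ_S = (6/π) × arcsin(ρ/2).

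For ρ = 0.3: ρ_S = 0.288, 1.96 / √0.712 = 2.32, α ≈ 2.0%.
For ρ = 0.7: ρ_S = 0.683, 1.96 / √0.317 = 3.48, α ≈ 0.05%.

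**Size by simulation.** 30 pairs, lognormal with log-SD 0.8, 20,000 replicates per cell, no change:

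| Correlation ρ | ρ_S | Formula, Mann-Whitney | Simulated, Mann-Whitney | Simulated, signed rank |
|---|---|---|---|---|
| 0.3 | 0.288 | 2.02% | 2.25% | 5.12% |
| 0.5 | 0.483 | 0.64% | 0.64% | 4.50% |
| 0.7 | 0.683 | 0.05% | 0.10% | 4.83% |
| 0.8 | 0.786 | 0.002% | 0.01% | 4.83% |

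A skewed integer score from 0 to 21 gives nearly the same: 2.0%, 0.6%, 0.05% and 0.0% for Mann-Whitney, against 3.9% to 5.3% for signed rank. At correlation 0.1 the Mann-Whitney size is about 3.9%. At −0.3 it rises to about 8%, so the conservative direction depends on positive correlation.

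**Power, Mann-Whitney vs signed rank (%).** Same 30 pairs, under three assumed forms of change:

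| Correlation | Lognormal, constant added, 0.2 SD | Lognormal, constant added, 0.4 SD | Lognormal, shift of 0.4 SD on log scale |
|---|---|---|---|
| 0.3 | 25 vs 26 | 77 vs 68 | 28 vs 36 |
| 0.5 | 22 vs 33 | 79 vs 79 | 25 vs 47 |
| 0.7 | 18 vs 49 | 84 vs 92 | 22 vs 67 |
| 0.8 | 15 vs 64 | 86 vs 98 | 19 vs 84 |

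The log-scale column used log-SD 1. For the integer score with a 1.6-point shift (about 0.4 SD), counting only samples that fail Shapiro-Wilk at either visit, the pairs are 39 vs 41, 38 vs 53, 35 vs 72 and 34 vs 88.

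The 9-point gain (77 − 68) arises from adding a constant to lognormal data, which moves a sharp lower bound. Shifts on the log scale gave losses in every cell checked at correlation 0.3 and above, up to 84 − 19 = 65 points in this table.

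**Which data reach this test.** At n = 30, Shapiro-Wilk rejects 96.6% of the lognormal samples and 77% to 80% of the integer-score baseline samples, but 5.0% of normal samples. Normal data would therefore mostly go to the paired t-test. Normality was checked on visit values; the SAP does not say whether visit values or differences are to be tested.

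**The case against.** The strongest reply is that this is a slip of naming. The between-arm sentence says Mann-Whitney, and the next sentence uses a label beginning with Wilcoxon and sets it beside the related-samples t-test. The author evidently had pairing in mind, the wording is permissive, and the safety section makes the right split. That is plausible. It still leaves a sentence naming the wrong test, and the SAP gives the data processing to staff not involved in patient management, who should be able to rely on the text.

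Second, type I error may be the less relevant quantity here. Both arms receive intensive rehabilitation, so within-arm change is expected with or without the drug. Within-arm p-values do not establish a drug effect in a two-arm trial in any case. This stands, and it limits the importance of the point.

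Third, the size of the effect rests on an unknown correlation. Entry is restricted to MoCA above 15 and up to 22, which tends to weaken correlation with later visits, so 0.7 to 0.8 cannot be presumed for that scale. The power figures also vary strongly with the assumed form of change. Both points stand: the tables show direction and range and do not predict this trial's results.

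Fourth, the safety paragraph names Friedman as well as signed rank, and most scales are measured at more than two visits. A signed rank test covers only a comparison of two visits. That is true, but the sentence at issue concerns before versus after, where signed rank is the counterpart of the paired t-test already named.

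**Conclusion.** The concern holds, as a minor point. As written, the SAP names an unpaired test as the only nonparametric option for paired within-arm comparisons, against its own description of that test and out of line with its safety section.

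Assuming 30 pairs, two-sided 0.05, no change and between-visit correlation of 0.3 to 0.8, the true error rate is about 2% down to 0.01%. The shortfall is small at correlation 0.1. With positive correlation the fault does not produce false claims of within-arm change. If change exists, the effect on power ranged from a gain of 9 points to a loss of 65 points over the assumed models, with losses in most cells and the largest at high correlation.

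Between-arm comparisons, safety parameters and indicators sent to the paired t-test are not affected.

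**What to change.** In the SAP sentence on within-arm comparisons, put the Wilcoxon signed rank test in place of Wilcoxon-Mann-Whitney, leaving the related-samples t-test as it is. Keep Mann-Whitney for comparisons between arms. This brings the sentence into line with the safety section for two-visit comparisons; where more than two visits are compared within an arm, that section already names Friedman.

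The cost is one term in one sentence, using a test the SAP already contains, and no new data. If within-arm tests have already been run with Mann-Whitney, re-run them with the signed rank test and disclose the change in the report.

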Study Protocol with Statistical Analysis Plan

Prospective Randomized Study of the modulating effect of MEXIDOL® as an adjuvant stimulant of the cognitive-emotional component of the rehabilitation treatment in patients with acute cerebral failure

NCT Number: NCT06221826

Pharmasoft
April 10, 2023

Study Protocol

The study procedures for the visits are presented in Table 1.

Conditions	Acute Cerebral Failure (Ischemic Stroke, Traumatic Brain Injury)
Study Design	Study Type: Interventional Primary Purpose: Treatment Study Phase: Phase 4 Interventional Study Model: Parallel Assignment Number of Arms: 2 Masking: None (Open Label) Allocation: Randomized (1:1) Enrollment: 60 [Actual] Time Frame: 66 days (I: parenteral therapy 10 days; II: oral therapy 8 weeks)
Arms	Mexidol and Standard Therapy Standard Therapy
Method of Application	Mexidol, solution for intravenous (IV) and intramuscular administration, IV 500 mg for 10 days, then Mexidol FORTE 250, film-coated tablets 250 mg, orally 1 tablet 3 times a day for 8 weeks.
Standard and Concomitant therapy	Standard treatment: basic practices of kinesitherapy, occupational therapy, speech therapy, clinical psychology, supplemented by adjuvant procedures of electrotherapy and rehabilitation environment therapy. The patient's rehabilitation load was at least 3 hours a day for 12 days. Patients may continue their pre-study therapy for other chronic conditions if, in the opinion of the investigator, they do not interfere with the results of this study and are administered at a stable dose during the study.
Primary Purpose	To evaluate the effect of pharmacological modulation of the rehabilitation process with the drug Mexidol as an adjuvant component of rehabilitation treatment of emotional and cognitive disorders in patients with Acute Cerebral Failure (Ischemic Stroke, Traumatic Brain Injury).
Secondary Purpose	To establish the possibility of identifying an individual clinical response to Mexidol therapy (responders and non-responders) and to determine indications for including the drug in an individual rehabilitation program.

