Exploratory Purpose	 To establish, using neurophysiological methods, the effect of the drug on perfusion-metabolic coupling (TCDG-EEG [transcranial dopplerography and electroencephalography] monitoring at the time of drug infusion) as an indirect indicator of increased metabolic activity of the brain. To establish, using clinical scales, the presence of a connection between the use of the drug Mexidol and the dynamics of recovery of the emotional-cognitive status of patients with acute cerebral insufficiency, during the period of permanent inpatient-outpatient rehabilitation treatment.
Research objectives (Outcome Measures)	1. Assessment of attentiveness and performance – the presence of the effect of Mexidol infusion on the change in the results of the Schulte test [work efficiency] before the start of the course, at the end of the

	course of infusion therapy and after the course of therapy with the			
	tablet form of Mexidol FORTE 250			
	Dynamics of cognitive status according to the Montreal Cognitive			
	Assessment (MoCA test)			
	3. Severity of depression according to the Beck Depression Inventory			
	(BDI scale)			
	4. Reduction in anxiety according to the Hospital Anxiety and			
	Depression Scale (HADS)			
	5. The degree of severity and dynamics of the Post Intensive Care			
	Syndrome (PICS) according to the PICS-score			
	6. Dynamics of level of mobility according to the Rivermead index			
	7. Dynamics of the level of life according to the Rehabilitation Routing			
	Scale (RRS)			
	8. Severity and dynamics of muscle strength according to the Muscle			
	Strength Quantitative Rating (MRC) Scale			
	9. Variants of specific dynamics of neurophysiological parameters of			
	perfusion (transcranial dopplerography) and metabolism			
	(electroencephalography) at the time of infusion of Mexidol (event			
	related monitoring)			
Safety and Tolerability	Incidence of Treatment-Emergent Adverse events related to Mexidol			
Criteria:	S			
Inclusion Criteria:	• ≥18 years old			
inclusion Criteria.	Signed Informed Consent Form			
	Acute Cerebral Failure (Ischemic Stroke, Traumatic Brain Injury)			
	 Montreal Cognitive Assessment (MoCA test) >15; ≤22 			
Evaluaion Cuitonio				
Exclusion Criteria:	• < 18 years old			
	• Epilepsy			
	• Pregnancy			
	Acute failure of one or more organ systems			
	 Purulent-inflammatory disease of any localization Participating in any other clinical trial 			

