Ethical and Lagal Aspects	This study will be conducted with the highest respect for the individual			
Ethical and Legal Aspects				
	participants in accordance with the requirements of this study protocol			
	and also in accordance with the following:The ethical principles that have their origin in the Declaration of			
	Helsinki.			
	International Conference on Harmonisation E6 Good Clinical			
	Practice: Consolidated Guideline.			
	All applicable laws and regulations, including, without limitation, privacy laws, clinical trial disclosure laws, and regulations.			
	privacy laws, clinical trial disclosure laws, and regulations.			

Table 1. Schedule of study procedures.

	Visit				
	Screening				
The study procedures		Visit 2 Day 1	Visit 3 Day 10	Video visit 4 Day 38	Visit 5 Day 66
Obtaining Informed Consent					
Checking inclusion/exclusion criteria		X			
Collection of anamnesis data					
Conducting a physical examination		X			
Measurement of BMI	X				
Body temperature	X				
Vital signs of the body's condition (mean BP, HR, RR)	X	X	X		X
Randomization		X			
The Rehabilitation Routing Scale (RRS)	X X		X	X	X
The Montreal Cognitive Assessment (MoCA test)			X		X
The Beck Depression Inventory (BDI scale)		X	X	X	X
The Hospital Anxiety and Depression Scale (HADS)		X	X	X	X
The Rivermead index		X	X	X	X
The Muscle Strength Quantitative Rating Scale (MRC)		X	X	X	X
The Post Intensive Care Syndrome (PICS) score		X	X	X	X
The Schulte test		X	X		X
Neurophysiological parameters (EEG, TCDG)		X			
Administration of the study drug intravenously		X	XX		
Dispensation of the study drug for oral administration			X		
Return of the drug and assessment of treatment compliance (if the drug is taken orally)					X
Question about the intake of concomitant drugs		X	X	X	X
Monitoring of adverse events		X	X	X	X

Statistical Analysis Plan

To create conditions for an independent assessment of the obtained results, statistical data processing at the end of the study will be performed by employees not involved in the management of patients participating in the study. Data processing will be performed in the software environment of the TIBCO® StatisticaTM v.13 and R v.4.4.1 and higher packages or similar, corresponding to the tasks of statistical analysis.

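### No primary scale, primary visit or multiplicity control: under assumed correlations, the chance of a false result favouring Mexidol is about 11–18% over ten emotional-cognitive tests, or 6.5–9% at Day 66 only, against 2.5% for one prespecified test

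*Combined protocol and SAP*

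**What the plan says.** The Primary Purpose concerns Mexidol as an adjuvant in "rehabilitation treatment of emotional and cognitive disorders in patients with Acute Cerebral Failure". That is a domain; it names no scale and no visit. The Outcome Measures list has nine numbered items: eight clinical scales and one neurophysiological item. None is marked primary. The Schulte test comes first and is the only scale with its own follow-up times (end of infusions, end of tablets), but it is not called primary. The Exploratory Purpose contains a very similar aim: "To establish, using clinical scales, the presence of a connection between the use of the drug Mexidol and the dynamics of recovery" of emotional-cognitive status.

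The SAP sets one threshold: "Statistically significant values are p-level <0.05". It does not say clearly which visits are tested:

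- Efficacy and safety indicators "will be presented using descriptive statistics by visits and therapeutic groups".
- By-visit testing is stated for one data type: "For study visits, qualitative (dichotomous) indicators will be compared between groups".
- For the scales the wording is permissive and names no visit: "Comparison of groups by quantitative indicators can be carried out" by t-test and Mann-Whitney test.

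The repeated-measures ANOVA in the safety section covers safety parameters only. The document contains no testing hierarchy, no multiplicity adjustment and no sample-size calculation from which an intended endpoint could be inferred.

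**The concern.** A plan with a stated primary aim should let a reader say beforehand which single result would support the aim and which would not. Here p<0.05 on any one of four scales, at whichever visit is tested, could be presented as meeting the Primary Purpose. Each extra comparison adds a chance of a false positive, and nothing in the plan limits the total.

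A reader shown every comparison could apply a correction (for ten tests, 0.05/10 = 0.005). The plan neither lists the comparisons nor requires a correction, so reporting a selected, unadjusted p<0.05 would comply with it. The trial is open label and has 60 patients, which makes prespecification one of its main protections against selective emphasis.

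**Working it through.** The plan gives no error rate or power figure to reproduce, so the check starts from the schedule of procedures (Table 1).

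**Inputs from the documents.** Threshold 0.05 per test (SAP). Post-baseline visits on Days 10, 38 and 66 (Table 1). Assessments marked at those visits:

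- Schulte 2 (Days 10, 66) and MoCA 2 (Days 10, 66)
- BDI 3 and HADS 3 (Days 10, 38, 66)
- Rivermead, MRC, PICS and RRS, 3 each

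Emotional-cognitive tests: 2 + 2 + 3 + 3 = 10. All eight scales: 10 + 4 × 3 = 22. HADS is counted once per visit.

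**Assumptions, because the documents are silent.** Two-sided tests, so 0.025 per test in Mexidol's favour. No true effect on any scale. Correlation between scales 0.2–0.7 and between visits 0.6–0.8; for different scales at different visits, the product of the two.

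**Independent tests.** P(at least one false result favouring Mexidol) = 1 − 0.975^k:

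- k = 1: 0.025
- k = 4: 0.096
- k = 8: 0.183
- k = 10: 0.224
- k = 22: 0.427

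For non-negative correlations these are upper bounds, and repeated measures on the same patients will not reach them.

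**Correlated tests.** Multivariate-normal simulation, 400,000 draws, critical value 1.96. Each entry is the chance of at least one false significant result favouring Mexidol.

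| Between scales / between visits | 4 scales, Day 66 | 10 tests | 8 scales, Day 66 | 22 tests |
|---|---|---|---|---|
| 0.2 / 0.6 | 0.092 | 0.178 | 0.163 | 0.321 |
| 0.3 / 0.7 | 0.088 | 0.161 | 0.152 | 0.279 |
| 0.5 / 0.8 | 0.079 | 0.131 | 0.125 | 0.213 |
| 0.7 / 0.8 | 0.065 | 0.111 | 0.094 | 0.164 |

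Under very strong correlation (0.9 / 0.9), ten tests give 0.071 and four scales at Day 66 give 0.047, still above 0.025.

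**Checks.** A separate simulation used one correlation for all pairs of different scales. It gave 0.181 to 0.107 for the ten tests, from within-scale 0.5 with between-scale 0.2 up to 0.7 for both. Simulated t-statistics with 30 patients per arm agreed (0.178 at 0.5 / 0.2 and 0.126 at 0.8 / 0.5).

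**Not counted.** Within-arm before-after tests, HADS subscales, the choice between t-test and Mann-Whitney, and the choice between values and changes. The figures are therefore not a ceiling.

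**The case against.** The strongest case on the other side has four parts.

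1. **The ten-test figure rests on the less well-supported reading.** The SAP states by-visit tests only for dichotomous indicators. This is right, and it is why the Day 66 figure is given as well. The listed Schulte follow-up times sit between the two readings: Schulte at both times plus the other three scales at Day 66 is five tests, giving about 8–11% under the same correlations (1 − 0.975^5 = 0.119 if independent). No reading returns to 2.5%.

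2. **The four-scale family is a judgement.** The documents assign no scales to the Primary Purpose. This also stands. Adding PICS makes 13 tests and about 15–22% (within-scale correlation 0.5–0.8, between-scale 0.2–0.5). The percentages illustrate the problem; the absence of a primary comparison does not depend on them.

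3. **Selective reporting is limited, because all efficacy indicators must be described by visit and arm.** That makes it harder to hide an unfavourable scale. It does not control which p-values are computed or emphasised, or the threshold applied to them.

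4. **This is a small open-label Phase 4 study with no power claim, so it may be read as exploratory.** The protocol separates Primary, Secondary and Exploratory Purposes and puts the emotional-cognitive aim first. Labelling the efficacy results exploratory would be an honest answer, but the plan does not do so.

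**Conclusion.** The concern holds and should be fixed before any efficacy claim is made. The plan has a stated Primary Purpose and a blanket 0.05 rule, with no endpoint, visit or error control linking them. The chance of a false result favouring Mexidol is about 11–18% if the four emotional-cognitive scales are tested at each post-baseline visit, and about 6.5–9% if they are tested only at Day 66. If all 22 scale-by-visit comparisons are allowed, it is 16–32%. The reference value for a single two-sided 0.05 test is 2.5%.

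These sizes depend on assumed two-sided testing, the assumed correlations and the choice of family. The direction does not: every family and every correlation setting examined exceeds 2.5%.

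**What to change.** First, state whether any aggregate comparison of outcomes between arms has been produced or reviewed. Staff seeing individual patients' results in an open-label trial is not such a comparison.

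- **If one has**, label all efficacy results exploratory. No other remedy remains.
- **If none has**, add one SAP paragraph before analysis. Name one primary scale and one primary time point (the sponsor's choice) for the between-arm comparison at two-sided 0.05. Only if that test is significant, test a short named list of emotional-cognitive secondaries under Holm at 0.05. Report all other scales, visits and within-arm changes as estimates with 95% confidence intervals and no significance claims.

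The gate matters. With one primary at 0.05 and three Holm secondaries tested regardless, the chance of any false positive in either direction is 1 − 0.95 × (1 − 0.05/3)^3 = 0.097 if independent, and 0.095 to 0.073 at between-scale correlation 0.2 to 0.7. Gated on the primary, it is 0.050 throughout. This holds only if the primary is chosen without knowledge of arm-level results, so the SAP should record who chose it and when.

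Also state how the emotional-cognitive aim under Exploratory Purpose differs from the Primary Purpose.

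The cost is one paragraph and no new data. The sponsor gives up isolated p<0.05 claims outside the hierarchy and can claim no secondary if the primary fails. With three secondaries, the smallest p-value must fall below 0.05/3 = 0.0167.

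### The only planned SAE summary counts SAEs the open-label investigator attributes to Mexidol; no row gives all-cause SAEs or deaths by arm

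*Combined protocol and SAP*

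**What the plan says.** The safety part of the Statistical Analysis Plan lists five parameters:

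1. "Total number of AEs, stratified by severity and frequency";
2. AEs that the investigator considers related to the study drug;
3. "Frequency of serious adverse events (SAEs), related, in the opinion of the physician-investigator, to the use of the study drug";
4. the share of patients with any AE;
5. the share of patients with two or more AEs.

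Row 3 is the only one that mentions serious events. The Safety and Tolerability entry of the Study Protocol carries the same causality restriction: "Incidence of Treatment-Emergent Adverse events related to Mexidol". Death is named neither as a safety parameter nor as an outcome in either part of the document.

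Three other statements bear on how row 3 will look. The Study Design entry gives no masking and 1:1 randomisation. The Arms entry reads "Mexidol and Standard Therapy Standard Therapy", so control patients receive standard therapy without Mexidol. The SAP also says: "Efficacy and safety indicators, as well as their changes, will be presented using descriptive statistics by visits and therapeutic groups".

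Table 1 has a row headed "Monitoring of adverse events", marked at Visits 2 to 5 (Days 1, 10, 38 and 66), with no restriction by arm or cause.

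**The concern.** A patient who never receives a drug cannot properly have an SAE related to it. The control entry in row 3 is therefore fixed at zero by definition, apart from misattribution. The Mexidol entry is the number of SAEs multiplied by the share that an investigator who knows the treatment attributes to it. Placing these two figures side by side looks like a randomised comparison but is not one.

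The patients have acute ischaemic stroke or traumatic brain injury and are followed for 66 days. In such a population, the randomised comparison of SAEs and deaths is the part of the safety evidence that does not rest on anyone's causal judgement. As written, the plan can be carried out in full without producing it. An excess, a deficit or no difference in SAEs on Mexidol could all lie behind the same published row.

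**Working it through.** **No figure to reproduce.** The plan states no SAE rate, attribution share or arm sizes, so the check is a reading of the five rows followed by an illustration.

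**Reading the rows.**

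| SAP row | Any cause? | Identifies SAEs? | Identifies deaths? |
|---|---|---|---|
| 1. All AEs by severity and frequency | yes | no | no |
| 2. Related AEs | no | no | no |
| 3. Related SAEs | no | related only | no |
| 4. Patients with any AE | yes | no | no |
| 5. Patients with two or more AEs | yes | no | no |

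No row is both all-cause and specific to serious or fatal events. Severity in row 1 is not a substitute: it grades intensity, whereas seriousness concerns the outcome or consequence of the event. The SAP itself uses the two terms separately.

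**Assumptions for the illustration.** 30 patients per arm (60 enrolled, 1:1) and at most one SAE per patient. The SAE counts are hypothetical.

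**Formula.** Newcombe interval for d = p1 - p2 (Mexidol minus control), built from the Wilson limits (l, u) of each proportion:

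lower = d - sqrt[(p1 - l1)² + (u2 - p2)²]; upper = d + sqrt[(u1 - p1)² + (p2 - l2)²]

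Wilson 95% limits for n = 30:
- 0/30: 0 to 0.1135
- 1/30: 0.0059 to 0.1667
- 3/30: 0.0346 to 0.2562
- 6/30: 0.0951 to 0.3731

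Worked once, for 3/30 versus 0/30:
- lower = 0.100 - sqrt(0.0654² + 0.1135²) = 0.100 - 0.131 = -0.031
- upper = 0.100 + sqrt(0.1562² + 0²) = 0.256

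**Same row, different all-cause results.**

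| Related-SAE row (Mexidol vs control) | Attribution of Mexidol SAEs | All-cause SAEs | Difference, points (95% CI) |
|---|---|---|---|
| 3 vs 0 | all related | 3/30 vs 0/30 | +10.0 (-3.1 to 25.6) |
| 3 vs 0 | all related | 3/30 vs 3/30 | 0.0 (-16.9 to 16.9) |
| 3 vs 0 | all related | 3/30 vs 6/30 | -10.0 (-28.5 to 8.8) |
| 0 vs 0 | none related | 6/30 vs 1/30 | +16.7 (-0.3 to 34.2) |
| 0 vs 0 | no SAEs | 0/30 vs 0/30 | 0.0 (-11.4 to 11.4) |

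**Dependence on attribution.** Suppose the SAE risk is 10% in both arms, so the true difference is nil, and a share q of Mexidol SAEs is judged related. The expected row is 30 × 0.10 × q Mexidol patients against 0 control patients. This runs from 0 vs 0 at q = 0 to 3 vs 0 at q = 1.

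**Would control SAEs occur at all?** The chance that a 30-patient arm has at least one patient with an SAE is 1 - (1 - p)^30. For assumed risks p of 2%, 5%, 10% and 20% it is 45%, 79%, 96% and over 99%. No listed row would identify those control-arm events as serious.

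**If the row were tested.** The SAP also says that dichotomous indicators will be compared between groups, and it does not exempt safety. Whether that reaches row 3 is unclear. If it did, the two-sided Fisher p-value would be 0.052 for 5 vs 0 and 0.024 for 6 vs 0. The second could arise with 6/30 SAEs in each arm if all six on Mexidol were judged related.

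**The case against.** The strongest reply is that control-arm safety data are not missing. Rows 1, 4 and 5 carry no causality restriction and are shown by group, so every control SAE is counted somewhere. A marked excess of severe events would show in row 1. In the 6/30 versus 1/30 example the related-SAE rows match those of a trial with no SAEs, but the full set of safety tables would not. This stands as a limit on the point: what is missing is a split by seriousness and fatal outcome, not adverse event data as such. It does not supply that split, because an unrelated SAE or a death enters those rows as one more AE.

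It can also be said that the list does not forbid further summaries, and that the protocol commits to Good Clinical Practice and disclosure law. That is fair. One cannot conclude that SAEs and deaths would go unreported, only that nothing in these documents plans their report by arm.

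Finally, the event risks and attribution shares are assumed, and a comparison of about 30 per arm is imprecise. Both are true. The figures show what the row cannot distinguish; they do not measure harm in this trial.

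**Conclusion.** The concern holds. The single SAE row is restricted by unblinded causal judgement and has a control entry that is zero by construction. No listed row gives all-cause SAEs or deaths by arm. This part rests on the text alone.

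The size is illustrative. With 30 per arm and at most one SAE per patient, one and the same row is compatible with all-cause differences at least from +10 to -10 points, and an empty row is compatible with +16.7 points. No SAE-specific test or risk difference is planned, so the fault is an uninformative display and a missing summary. A misleading test would follow only if the general between-group rule were applied to this row. The efficacy analyses, sample size and significance level are not affected. The plan should be changed, but the gap does not undermine the trial as a whole.

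**What to change.** Add to the SAP safety list: number and proportion of patients with any SAE, and number of deaths, by arm, regardless of causality, Day 1 to Day 66. A risk difference with a 95% confidence interval is preferable to counts alone. Keep related AEs and related SAEs as a descriptive summary of the Mexidol arm, and state that the general between-group test is not applied to them. The protocol safety criterion need not be rewritten. Enrolment is already given as actual, so if the row is added after enrolment, label it so.

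The cost is one or two table rows, provided seriousness and outcome were recorded for every AE in both arms. Table 1 schedules AE monitoring without an arm restriction but does not say which attributes are recorded, so this must be confirmed.

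The drawback is low precision. At 3/30 in each arm the interval is -16.9 to 16.9 points. Exact two-sided Fisher power at the 0.05 level is 10% for true risks of 20% versus 10%, and 37% for 30% versus 10%. The text should say that a non-significant difference is not evidence of safety.
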